## 11.4 Recording of an Adverse Event

Adverse events will be recorded for the duration of a patient's study treatment, and for up to 30 days following the last study treatment. All AEs, regardless of causal relationship are to be recorded in the CRF and source documentation. Additional information about each event, such as treatment required, eventual outcome, and whether or not therapy had to be interrupted or dosages reduced, will also be recorded on the CRF.

Pre-existing conditions will be recorded at baseline on the Medical History Form. If a pre-existing condition does not change, it does not have to be reported as an AE on subsequent cycles.

## 11.5 Serious Adverse Event Reporting

All SAEs will be reported by email or facsimile upon becoming aware of the event within 24 hours to Gradalis, Inc. This includes any death from any cause while a patient is receiving treatment (Vigil™) on this protocol, or  $\leq$  30 days following the last dose of protocol treatment (Vigil™).

The site will supply as much information as is available at the time of the initial facsimile (study number, patient initials, patient study number, onset date, relationship, patient demographics, event, dosing regimen of study agent) to:

## 12.0 PATIENT COMPLETION AND WITHDRAWAL

### 12.1 Indication for Taking Patients Off Study

The Investigator must notify the sponsor at any time following discontinuation of a patient on study for the occurrence of a serious or unexpected AE associated with the use of the study medication.

## 13.0 DATA EVALUATION

### 13.1 Statistics and Estimated Sample Size

The primary objective of this study is to investigate whether maintenance Vigil™ vaccine after a clinically defined complete response to induction platinum/paclitaxel chemotherapy results in prolonged time to recurrence (TTR) compared with standard of care observation. TTR was used for the purpose of sample-size estimation. Based on prior published experience (Markman, Liu et al. 2003), the median RFS after a clinical complete response to induction therapy for the control arm was estimated to be approximately 16 months for those with stage IV or suboptimal (> 1 cm residual) stage III disease and 24 months for stage III patients with optimal (< 1 cm residual) disease. Given an average RFS of 24 and 16 months, respectively, a 10% increase in RFS (i.e. TTR) would provide adequate statistical power to support expanding the study (Table 6). This analysis was performed using a statistical power calculator (<http://www.dssresearch.com/KnowledgeCenter/toolkitcalculators/statisticalpowercalculators.aspx>) to conduct a 1-tail test of a sample average in comparison to the historical value, a standard deviation of 1.0, and an alpha error level of 5%. In order to expand the protocol treatment base and increase the rate of accrual while maintaining the objectives of the protocol, the study, which was initially limited to patients with stage IIIC ovarian cancer, is being expanded to patients with Stage III/IV disease. In the SEER database: 1988-2001(Kosary 1988-2001), women with Stage IIIC disease comprised 19.4% of the ovarian cancer population; those with Stage III inclusive, 35.3%; and those with Stage IV, 31.7%. Thus, the eligibility expansion increases the base catchment population from 19.4% of women with ovarian cancer to 67% of which only a subset will meet protocol criteria.

In the completed Phase I study of Vigil™ vaccine in patients with solid tumors experiencing progressive disease following prior therapy, 50% of patients with serial assessments (n=18) demonstrated conversion from  $\gamma$ IFN ELISPOT

negative to positive by Month 4 (Senzer N 2012). The percent  $\gamma$ IFN ELISPOT conversions and the timing thereof will be recorded in the current patient population of patients with minimal or no residual disease using descriptive statistics to assess the hypothesis that there is an inverse relationship between tumor volume and immune responsiveness based in part on the quantitative relationship between tumor volume and the production of immunosuppressive factors.

Although all patients will be evaluated for RFS, subgroup analyses will be separately performed on patients with negative ELISPOT at baseline and those with positive ELISPOT at baseline.

**Table 6:** Statistical Power of 2:1 Randomization Trial per Surgical Stage Stratification Group (1 tailed t test)

Surgical Stage Stratification	Vigil™ Vaccine (TTR in months)	Observation Control (TTR in months)	Power	n
Stage III patients with optimal (< 1 cm residual)	26.4	24	1.0	30
Stage IV or suboptimal (> 1 cm residual) stage III disease	17.6	16	1.0	30

Exploratory analysis of two Phase III studies (D9901 and D9902) with the recently FDA approved Provenge documented prolonged survival benefits in Provenge-treated prostate cancer patients (25.9 months vs. 21.4 months and 25.8 vs. 21.7 months, respectively). Supporting our clinical objective, patients who subsequently received docetaxel experienced a median survival of 34.5 months compared to 25.4 months in patients treated with placebo followed by docetaxel. Descriptive statistics will be employed to format the response rates and response durations to 2nd line therapy in patients that relapse in both FANG™ and observational groups.

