## SYNOPSIS

**Summary:** Despite a gradual improvement in their overall survival over the past decade, approximately 75% of women with Stage IIIC ovarian cancer who achieve a complete clinical response will relapse as will 50% of those achieving pathologic complete response at a median time of 18-24 months. Phase III studies of both maintenance and consolidation therapeutic interventions have not translated into an overall survival advantage. Preliminary studies of immunotherapy in patients with ovarian cancer suggest target accessibility (potential immunogenicity) to immune mediated approaches. In an effort to overcome limitations of immunostimulatory cancer vaccines, we designed a novel autologous whole cell vaccine, Vigil™ formerly known as FANG™, incorporating the rhGMCSF transgene and the bifunctional shRNAfurin (to block proprotein conversion to active TGFβ1 and β2) to 1) address the inability to fully identify cancer associated antigens, 2) effect antigen recognition by the immune system (i.e. antigen→immunogen), 3) enhance effector potency, and 4) subvert endogenous cancer-induced immune resistance.

A Phase I assessment of Vigil™ vaccine in 33 advanced solid tumor patients (1 of them being a pediatric patient 15 years of age) receiving ≥1 vaccination (at a dose of  $1.0 \times 10^7$  or  $2.5 \times 10^7$  cells/injection/month for a maximum of 12 vaccinations) demonstrated safety of the Vigil™ vaccine. Furthermore, proof of principle was established in the manufactured vaccines with increased mean GMCSF expression post-transfection to  $1135 \text{ pg}/10^6 \text{ cells/ml}$  and knockdown of furin, TGFβ1 and TGFβ2 at 78%, 93%, and 95%, respectively). In addition, although a Phase I study, the data suggested an overall survival benefit.

Given the preliminary Phase II evidence of prolongation of time to relapse in randomized Vigil™ vs. No Vigil™ treated patients ( $p=0.005$ ), as of this amendment all patients screening for enrollment into the main portion of the trial (including those who previously had tumor tissue harvested), will receive Vigil™ vaccine and will no longer be randomized. An extensive Phase II/III protocol is designed to more definitively assess benefit. Additional safety data in ovarian cancer patients receiving  $1 \times 10^7$  cells/ID injection on a monthly basis (maximum 12) is required.

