**Objective(s):****Primary Objectives:**

- To assess time to recurrence (TTR) following the administration of bi-shRNAfurin and GMCSF autologous tumor cell (Vigil™) vaccine.

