**Methodology:**

This is a Phase II open-label trial of Vigil™ autologous tumor cell vaccine. Tumor will be harvested at the time of surgical debulking (standard of medical care).

Patients achieving clinical complete response (CR) following primary surgical debulking and doublet chemotherapy will be stratified for i) surgical stage (Stage IV or suboptimal debulking (>1 cm residual) Stage III disease versus Stage III patients with optimal debulking (<1 cm residual)) and ii) post-operative chemotherapy, pre-vaccine CA-125 of greater than 10 but less than or equal to 20 U/mL versus 0≤10 U/ml then randomized 2:1 (Note: patients with Stage IIIC ovarian cancer will be additionally evaluated as a subset using descriptive statistical endpoint only). Patients will receive  $1.0 \times 10^7$  cells / intradermal injection of gene transfected autologous tumor cells, Vigil™, once a month for up to 12 doses as long as sufficient material is available. A minimum harvest aliquot to produce 4 monthly injections will be required for entry into the study. These patients will be managed in an outpatient setting. Hematologic function, liver enzymes, renal function and electrolytes will be monitored monthly. Immune function analysis including ELISPOT analysis of cytotoxic T cell function to autologous tumor antigens will be monitored at (≤24 hours before) tissue harvest, ≤24 hours before the first cycle chemotherapy (post debulking), ≤24 hours before the third cycle chemotherapy (post debulking), baseline (screening); prior to Vigil™ injection at Months 2, 4, 6 and EOT. CA-125 will be monitored at baseline, every month for the first year, every 3 months ± 2 weeks for the second and third year.

**Number of Patients:** Approximately fifty (50) patients with high risk Stage III/IV ovarian cancer.

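### Randomization has been stopped, but Section 13.1 still compares TTR with observation, without saying which patients enter or when TTR starts for observation patients

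*Combined protocol and SAP*

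**What the plan says.** **Randomization stops.** The Synopsis summary cites "preliminary Phase II evidence of prolongation of time to relapse in randomized Vigil™ vs. No Vigil™ treated patients" (p=0.005). On that basis patients screening from this amendment on ("including those who previously had tumor tissue harvested), will receive Vigil™ vaccine and will no longer be randomized") all get vaccine. It adds "An extensive Phase II/III protocol is designed to more definitively assess benefit" and says that more safety data are needed.

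**Randomization continues.** The Synopsis Methodology still has patients stratified, "then randomized 2:1 (Note: patients with Stage IIIC ovarian cancer will be additionally evaluated as a subset using descriptive statistical endpoint only". Section 4.1 says the same, and Section 5.1 says that about 50 patients will be randomized. Section 5.2 ends stratification.

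**Primary objective.** The Synopsis and Section 3.1 give it without a comparator: "To assess time to recurrence (TTR) following the administration of" the vaccine. Section 13.1 gives it as a comparison: whether maintenance Vigil "results in prolonged time to recurrence (TTR) compared with standard of care observation".

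**Sample size.** Section 13.1 describes a calculator run for a "1-tail test of a sample average in comparison to the historical value", with SD 1.0 and 5% alpha. Table 6 presents the result as a 2:1 randomized trial analysed by a one-tailed t test, with an observation column and power 1.0 in each surgical stage group.

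**TTR.** Section 8.1 starts it at first treatment and ends it at objectively documented recurrence. Section 13.3 starts it at first dose and also counts death from any cause. Neither gives a censoring rule; Section 13.4 gives one for time to treatment failure only.

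**The concern.** A primary comparison needs a population, a time origin shared by both arms, an event definition and a test. Section 13.1 keeps the comparison, but the text does not supply these for the trial as it now stands. Patients who enter after the amendment have no concurrent control, and nothing says whether they belong in the comparison. Patients already assigned to observation have no first dose in the text, so the stated TTR rule cannot be applied to them.

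The timing makes this matter more. The arms have already been compared once, in a look that Section 13 does not mention. Population, origin and test would now be chosen by people who know how that look came out. Unless the amendment fixes them and says when they were fixed, a reader cannot tell a planned analysis from one selected after the fact.

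**Working it through.** **1. Where the current text conflicts**

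| Item | One statement | Another statement |
|---|---|---|
| Allocation | Synopsis summary: no more randomization | Synopsis Methodology, 4.1: 2:1; 5.1: about 50 randomized |
| Stratification | 5.2: ended | Synopsis Methodology, 4.1: still done |
| Primary objective | Synopsis, 3.1: no comparator | 13.1: versus observation |
| TTR start | 8.1, 13.3: first treatment or first dose | Observation arm: none given |
| TTR event | 8.1: recurrence | 13.3: recurrence or death |

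**2. Can Table 6 settle the intended analysis?** Inputs from Section 13.1: gains of 26.4 − 24 = 2.4 and 17.6 − 16 = 1.6 months, SD 1.0, one-sided 5%, n = 30 per group.

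- Two-sample, 20 v 10: Φ(δ/√(1/20 + 1/10) − 1.645). For 2.4: Φ(6.197 − 1.645) = 0.99999. For 1.6: Φ(4.131 − 1.645) = 0.994 (noncentral t gives 0.991).
- One-sample, n = 30, against a fixed value: Φ(δ√30 − 1.645). For 2.4: Φ(13.145 − 1.645); for 1.6: Φ(8.764 − 1.645). Both exceed 0.9999.

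Both readings round to the printed 1.0, because SD 1.0 makes either gain enormous. The arithmetic cannot show which was used.

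**3. How much can the time origin matter?** Section 6.4 allows first dose from 3 weeks (21/30.44 = 0.69 months) to 2.5 months after chemotherapy. Suppose, for illustration, that the clock ran from end of chemotherapy in one arm and from first dose in the other. A 2.5-month offset is 2.5/1.6 = 156% or 2.5/2.4 = 104% of the gain sought. The unstated origin can be as large as the planned effect.

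**4. What information does the randomized comparison carry?** The number randomized and the follow-up are not given. Assumed: 30 randomized 2:1, exponential TTR, medians 24 and 16 months (Section 13.1) in equal shares, 36 months of follow-up, and HR 1/1.1 for the 10% gain.

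- Events: 30 × ½[(1 − 2^(−36/24)) + (1 − 2^(−36/16))] = 30 × ½(0.646 + 0.790) = 21.5.
- Power (Schoenfeld, one-sided 5%): Φ(ln 1.1 × √(21.5 × 2/9) − 1.645) = Φ(0.0953 × 2.188 − 1.645) = Φ(−1.436) = 7.5%.
- HR detectable with 80% power: exp(−(1.645 + 0.842)/2.188) = 0.32.
- Events needed for 80% power at HR 1/1.1: (1.645 + 0.842)²/[(ln 1.1)² × 2/9] ≈ 3,063.

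Range: 21 randomized with an 80% optimal-debulking share gives 14.2 events, 7.0% power and a detectable HR of 0.25. Fifty randomized with a 20% share gives 38.1 events, 8.6% and 0.43.

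**The case against.** **Much of this is transition wording.** Randomization stops only for patients screening from the amendment on. Section 13.1's mention of an observational group and Section 6.1's conditional reference to randomization are therefore correct for patients already randomized. That stands, and neither is counted as a fault. It does not reach Sections 4.1, 5.1 and 13.1, which describe the whole trial as randomized.

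**A reader might infer a third planned analysis, a test against a historical value.** The documents do not support this. The sentence describes how a power calculator was run. It conflicts with Table 6's title, but it is not a plan to test TTR. Nor can one say that Table 6 came from that run, since either reading gives 1.0.

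**A reader might infer that later Vigil-only patients will be pooled with the randomized Vigil arm.** No section proposes it, and the pointer to a separate Phase II/III protocol suggests a descriptive role for them. The fault is only that the population is unstated.

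**A reader might say that the comparison cannot be done at all.** The Synopsis reports one, so some start date was used; it is undocumented. That observation patients have no first dose is an inference: no section gives them one or describes crossover.

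**This is an open-label Phase II, with definitive assessment deferred.** True, and it lowers the severity. Section 13.1 nevertheless still calls the comparison the primary objective.

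**Conclusion.** The concern holds as a fault of definition and consistency. The primary comparison in Section 13.1 has no documented time origin for observation patients and no stated population, the objective is worded in two ways, and the design sections still randomize after the Synopsis has stopped it. The p=0.005 look is not provided for in Section 13. It is read here as a look at this trial's own randomized patients, because it is the stated reason for ending this trial's randomization.

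Nothing here shows that the p=0.005 result is biased, and the text does not allow that conclusion. The low power does not contradict a small p-value either: at about 22 events only a large observed effect would produce one, and neither the events nor the estimate is reported.

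The textual fault rests on no assumption. The figures of about 22 events and 7.5% power rest on the assumed number randomized, follow-up, stage mix and exponential TTR; across the ranges tried for number randomized and stage mix, power stays at 7.0–8.6%. Severity: should be fixed.

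**What to change.** 1. In the Synopsis objectives and Sections 3.1 and 13.1, state one objective in two parts. Comparative: TTR, Vigil versus observation, in patients randomized before the amendment. Descriptive: TTR in patients entered after it.
2. Analyse the randomized patients as randomized, by log-rank and Cox stratified by the original randomization factors, with TTR from randomization in both arms. State which factors were used: Section 4.1 names surgical stage and CA-125, while Section 5.2 lists chemotherapy route beside them. Say that this origin and test were set after the p=0.005 look. Report TTR from first dose in the Vigil arm as a description.
3. Describe later Vigil-only patients by Kaplan-Meier with 95% CI from registration, without pooling and without a test against observation or against 16/24 months.
4. Amend Sections 8.1 and 13.3 to give these origins, settle whether death is a TTR event, and add a censoring rule.
5. Label the historical-value sentence and Table 6 as the original sample-size calculation only.
6. Disclose the p=0.005 look (data cut-off, events, test, sidedness) as not provided for in Section 13.
7. Reconcile the randomization and stratification wording in the Synopsis (Methodology, Inclusion Criteria), Sections 4.1, 5.1, 6.1, 6.4 and 6.6, and Appendix B. In Section 5.1, do not imply that about 50 were randomized. In the exclusion criteria (Synopsis and 5.3), reconcile the time anchor so that it also applies to patients who are registered but not randomized, leaving the clinical rule unchanged.

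**Cost.** Amendment wording and one descriptive analysis; no added patients. The plan must say openly that the randomized comparison carries little information for the protocol's 10% effect. The log-rank p-value will also be approximate at this size: simulated at 20 v 10 with no true effect, the one-sided 5% test rejects about 6% of the time.

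### Section 13.1 sizes the trial on a test of a mean time to recurrence against a historical median; if the vaccine-only patients were tested that way, the one-sided error would not be 5%

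*Combined protocol and SAP*

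**What the plan says.** Section 13.1 states the aim as finding out whether maintenance vaccine "results in prolonged time to recurrence (TTR) compared with standard of care observation". It takes its control figures from a published trial: "the median RFS after a clinical complete response to induction therapy for the control arm was estimated to be approximately 16 months" for stage IV or suboptimally debulked stage III disease, and 24 months for optimally debulked stage III. The next sentence uses the same two numbers under another name: "Given an average RFS of 24 and 16 months, respectively, a 10% increase in RFS (i.e. TTR) would provide adequate statistical power". The calculation is then described as one "to conduct a 1-tail test of a sample average in comparison to the historical value", with "a standard deviation of 1.0, and an alpha error level of 5" per cent.

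Table 6 reports that calculation as "Statistical Power of 2:1 Randomization Trial per Surgical Stage Stratification Group (1 tailed t test"). It sets 26.4 against 24 months and 17.6 against 16 months, and gives power 1.0 with n = 30 in each row.

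The Synopsis says that patients screened from this amendment on "will receive Vigil™ vaccine and will no longer be randomized", although its Methodology paragraph and Section 4.1 still describe 2:1 randomization. The planned size is "Approximately fifty (50) patients with high risk Stage III/IV ovarian cancer".

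Section 13.3 defines time to recurrence (TTR) from first dose to recurrence or death. It gives no censoring rule, although Section 13.4 gives one for time to treatment failure. No log-rank, Kaplan-Meier or Cox analysis of TTR is named in the text provided.

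**The concern.** A median has been used as the null value for a mean. The two agree only when the distribution is close to symmetric, and times to recurrence are usually right-skewed. If the vaccine does nothing, the true mean TTR then lies above 16 or 24 months, and a one-tailed test of the sample average tends to reject because of the shape of the curve. If follow-up is short and unfinished times are averaged as they stand, the bias can run the other way.

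This matters because TTR is the sole primary objective and the patients now entering have no concurrent randomized control. A comparison with a historical value is the form open to them, and this is the only one-sample TTR test that the plan describes.

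**Working it through.** **Inputs.** From Section 13.1 and Table 6: benchmarks 16 and 24 months, a 10% increase (differences 1.6 and 2.4 months), SD 1.0 (no unit given; months assumed), one-sided alpha 5%, n = 30 per stage group. From the Synopsis: about 50 patients in all. The documents give no distribution for TTR, so exponential and Weibull shapes are assumptions.

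**1. The plan's own figure.** One-sample power is Φ(δ√n/SD − 1.645).
- 24-month group: 2.4 × √30 = 13.15, so power 1.000.
- 16-month group: 1.6 × √30 = 8.76, so power 1.000.

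Read as a two-sample 2:1 test with 20 + 10 patients, the standard error is √(1/20 + 1/10) = 0.387, and power is 1.000 and 0.994. Either reading reproduces the stated 1.0, so the figure does not show which test was meant.

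**2. Mean against median.** For exponential times, mean = median / ln 2. This gives 16 / 0.693 = 23.1 months and 24 / 0.693 = 34.6 months, each 44% above the value used as the null.

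**3. How many vaccinated patients per group.** Table 6 does not say whether 30 counts vaccinated patients only or both arms.
- All 30 vaccinated: 30.
- 30 split 2:1: 20.
- 50 split evenly over two groups, all vaccinated: 25.
- The same 25 split 2:1: about 17.

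**4. False-positive rate of the one-sample test.** Simulated with at least 100,000 trials per setting, true median equal to the benchmark, nominal one-sided 5%.

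| Assumption | n per group | Rejection with no effect |
|---|---|---|
| Exponential, complete follow-up, sample SD | 17 / 20 / 25 / 30 | 26% / 32% / 41% / 49% (both groups) |
| Weibull shape 1.5, same | 20 / 25 / 30 | 17% / 20% / 24% |
| Weibull shape 2, same | 17 to 30 | 9-13% |
| Exponential, capped at 36 months and averaged as observed, 16-month group | 20 to 30 | 17-22% |
| The same cap, 24-month group | 20 to 30 | 1-2% |
| Exponential, complete follow-up, SD 1.0 taken as known | 17 to 30 | 89-96% |

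The 36-month cap matches the three years of scheduled CA-125 monitoring. It lowers the mean to about 18.2 months in the 16-month group and 22.4 in the 24-month group, which is why the second group falls below 5%.

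**5. The two-sample reading.** A 2:1 two-sample t test on exponential data with no effect rejects in 3.9-4.0% of trials at 20:10 and 4.2-4.3% at 33:17. It compares mean with mean, so the bias disappears.

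**6. A matched test.** The one-sample log-rank test against the correct exponential curve, with 17-30 patients and times either complete or censored at 36 months, gives about 3.4-4.0% when the variance is E and 4.6-5.6% when it is (O+E)/2. (O and E are observed and expected events.)

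**7. Power once mean and median are not confused.** With exponential times and complete follow-up, an exact exponential test at the planned 10% increase has power of about 12% at n = 20 and 14% at n = 30, against the stated 1.0.

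**The case against.** The strongest reply is that the sentence describes a sample-size calculation already done on a web calculator, and nothing says that trial data will be tested this way. The objective in Section 13.1 and the title and control column of Table 6 point to a randomized comparison with observation, where the bias does not arise. The Synopsis also cites a between-arm result (p = 0.005), so such a comparison has been made. The size of any error depends on a TTR distribution that the plan never states.

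Much of this stands. A reader might infer that the plan's only efficacy test declares an inert vaccine beneficial 40-50% of the time in each stage group. The documents do not support that. The randomized reading is also on the page, no decision rule is stated, and 40-50% needs exponential times, complete follow-up, the sample SD and 25-30 vaccinated patients per group. Nor do they say that this test decides whether the study expands: the expansion that Section 13.1 goes on to describe is of eligibility, from stage IIIC to stage III/IV.

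What remains is that the text and the table describe two different tests for one calculation, that the one-sample version has the wrong null value, and that no alternative is given for patients without a randomized control.

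**Conclusion.** The point holds as an error in the stated method. Historical medians are relabelled as averages and used as the null for a test of a mean, and neither this test nor the t test in Table 6 allows for censored times.

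Its consequence is conditional. If the vaccine-only patients were tested as described, the one-sided error would be about 26-49% with exponential times, complete follow-up, the sample SD and 17-30 vaccinated patients per group. It would be about 9-13% with Weibull shape 2. With a 36-month cap and 20-30 patients it would be 17-22% in the 16-month group and 1-2% in the 24-month group. With the stated SD of 1.0 taken as known and exponential times, it would be 89-96%. The rate depends on curve shape and follow-up and is not controlled at 5%. A two-sample 2:1 comparison of the randomized patients is not affected.

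**What to change.** In Section 13.1 and Table 6:

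- Call 16 and 24 months medians throughout, and remove the t test of a sample average against them.
- For patients treated without randomization, specify a one-sample log-rank test against the benchmark curve for each patient's surgical-stage group, with observed and expected events summed over both groups. State the assumed curve shape, a sensitivity shape and the variance used, for example (O+E)/2. Censor recurrence-free patients at last assessment, and report the Kaplan-Meier median with its 95% CI beside the benchmark.
- For randomized patients, specify a log-rank test stratified by surgical stage.
- Recompute the power in Table 6 for these tests, and say whether n counts vaccinated patients or both arms.

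This needs rewording and one recalculation, with no new patients or data. There are two downsides. The stated power becomes much less favourable, and the one-sample test rests on a benchmark curve shape that the documents do not supply.
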